16. “I can relate to this quote; I used to have similar responses. I used to find pleasure in harming myself. I used to cut myself for a long time.” **Response:** Thank you for sharing your experience. It is possible that many other group members have had similar experiences. It may be useful to you and the group to share your story.

17. “I just don’t feel worthy as person, no one is ever going to love me or care about me.” **Response:** We recognize that these are strong emotions. If you feel comfortable, we recommend that you share these thoughts with the group. The therapist will call you this week to check in.

18. “I can really relate to that—I have trouble setting boundaries in relationships...People walk all over me; I’m weak.” **Response:** We think you are a very strong person for openly talking about your feelings and emotions. We encourage you to share your response with the group next session.

19. “The sessions are becoming very stressful for me; I find myself feeling upset when I leave.” **Response:** Thank you for sharing this. We want to do whatever we can to make this a more positive experience. The therapist will call you this week to check in.

20. “I can relate to this quote, I don’t know what’s to become of my future...I am a complete failure.” **Response:** Thinking about the future can evoke uncertain feelings. Others may be experiencing similar feelings; it may be valuable for you to address these concerns in the session.

Adverse Events

This study carries some risk for the development of suicidal ideation, suicide attempts, and self-mutilation as adverse events because the women eligible to participate have PTSD or a history of violent trauma. In order to address this risk, we will evaluate potential development of these adverse events at baseline, 8 weeks, and the 3-month follow-up, as well as informally monitoring participant condition on a weekly basis. Participants in the wait-list group will also be assessed for adverse events over the phone at 3 weeks and 6 weeks after the start of treatment for the intervention group. Participants will also be asked to keep a Weekly Adverse Event Log to

measure safety outcomes. In addition, since our screening measures may detect suicidal risk and intimate partner violence, we will also provide appropriate care as necessary. We will use the following assessments to assess risk:

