- (2) have a current diagnosis of PTSD (As determined by the Clinical Administered PTSD Scale to diagnose PTSD resulting from trauma that occurred in the past 30 days; this structured interview measures the symptoms of PTSD corresponding to DSM–IV criteria)

Women who meet the threshold criteria will be invited to participate in the first step of the study: participation in the Asian Women Discussion group, which consists of 10 psychotherapy sessions and an additional post-intervention meeting. This focus group will provide crucial feedback to help refine the sessions. Because only ten women who meet the eligibility guidelines will be selected: most women will not be selected.

F.3. Exclusion criteria (Indicate if you have different exclusion criteria for different cohorts)

Exclusion criteria. Women who meet any of the following criteria will be ineligible for the study:

- (1) Significant current risk of homicidal or suicidal behavior (deliberate self-injury where there is at least some admitted or inferred intention to die; particularly, participants who have had a suicide attempt within the past year or participants with active suicidal ideation with intent or plan)
- (2) Presence of schizophrenia, schizoaffective, or organic mental disorders using DSM-IV criteria
- (3) Women of mixed race (i.e., those who do not identify as 100% Chinese, Korean, or Vietnamese or a mixture thereof)
- (4) Victims who have experienced natural disasters or other non-violent trauma only (i.e., those who have not been traumatized by physical or sexual violence)
- (5) Women who are currently victims of severe Intimate Partner Violence (IPV) using The Revised Conflict Tactics Scale (CTS2).
- (6) Women who experience worse outcomes than baseline two weeks after the study begins will be withdrawn from the study.

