(3) Safety analysis (Hypotheses for safety): For the safety measure, participants will be asked to keep a Weekly Adverse Event Log for measuring safety outcomes (including IPV, suicidal ideation, suicide attempts, and self-mutilation). Our hypotheses are: (A) The AWARE group will have statistically significant lower proportions of suicidal ideation, suicide attempt, and self-mutilation at 8 weeks and 3-month follow-up, compared to baseline. (B) There will be no increased frequency of IPV among the AWARE group between the baseline and post intervention. McNemar's tests will be used to test both (A) and (B). Safety outcomes are measured as developments of adverse event outcomes over the course of the study. These include: (1) suicidal ideation, (2) suicide attempts, (3) self-mutilation, (4) and frequency of IPV. We will estimate the proportion of each adverse event at 95% confidence intervals for participants in the intervention group. We will employ McNemar's tests to compare the proportions of each adverse event in the AWARE group at baseline to the ones in the wait-list group. In addition, mixed effects models for adverse event outcomes will be performed, adjusting for baseline characteristics, such as psychiatric diagnosis severity and substances use, to measure the impact of the baseline characteristics on adverse events and also the pattern of change in adverse events from baseline to the post-intervention follow-up.

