Evaluation of Pilot RCT Analysis: We will use an intention-to-treat (ITT) analysis, which indicates all women who are randomized will be included for analysis. To test the success of the randomization, prognostic factors including baseline education, psychiatric diagnosis severity, and substance use will be compared between participants in the intervention group and wait-list group using chi-square tests. Baseline characteristics that show imbalance between groups will be adjusted in multivariate regression models. The efficacy outcome variables will be analyzed as either dichotomized or continuous variables. For PTSD, continuous measures of the CAPS will be assessed. In order to sensitively capture any changes in PTSD scores, continuous measure will be chosen. For HIV outcomes, we will use both dichotomous and continuous variables to measure status and severity of the outcomes at baseline, 8 weeks, and 3-month post-test. Mixed effects models will be used to compare the pattern of change in dichotomous and continuous outcomes over time between groups using normal and logit links, respectively. We will first use an unstructured covariance matrix to

account for correlation between repeated measurements in the same participant and compare it to other covariance structures, using goodness of fit. The most suitable covariance matrix will be chosen for the final model. The same approach will be followed for secondary outcomes. All statistical testing will be performed at the significance level of 0.05 using SAS 9.3.102. Additionally, in order to explore whether compliance affects outcome measures, we will compare the sexual risk behavior, psychiatric severity, and substance use measures between those who drop out versus those who complete the intervention using two-tailed, independent samples t-tests.

Data analysis for Aim 3 (year 2 and 3):

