All sessions will be led by a licensed therapist. These sessions will be recorded and safely stored in a password-protected server, and therapists will work closely with and be monitored by the principal investigator. Participants will be asked to read and sign statement of informed consent explaining privacy protections and confidentiality protections. If participants experience discomfort and wish to discontinue the treatment, they will be able to withdraw from the study or refuse to complete a session. Additionally, if participants begin to show symptoms of depression, self-harm, or suicidality, that the therapist leading the group believes warrants treatment they will be withdrawn from the study and referred to a hospital for alternative treatment, which includes treatment at BU Medical Center (BUMC), South Cove Community Health Center, or South Shore Mental Health, the latter two where we have advisors ([name] and [name]).

During the course of each SS session, the therapist will take note of each participant to ensure that none exhibit traits of a deteriorating condition. Participants in crisis (e.g. exhibiting symptoms of imminent risk to self or others, psychotic symptoms, safety concerns) will be immediately referred to a hospital to ensure proper treatment and safety. Participants who are not deemed to be in an emergency situation but are showing symptoms of deterioration (as determined by the licensed therapist) will be closely monitored and, if appropriate, considered for referral for alternative treatment. All decisions will be made jointly by the therapist and the principal investigator.

“AWARE Stories” via secure mobile messaging. We aim to enhance the quality of our mental health intervention by supplementing it with a secure messaging application. We will write and use text messages that are closely tied with our weekly session topics to stimulate aspects of psychotherapy outside the weekly group sessions. We will utilize Doc Halo, a secure mobile messaging application, and SMS as message delivery platforms. Participants will be given the

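### Women who get worse are withdrawn from the study itself, with no provision for their 8-week and 3-month assessments, so outcomes are lost on those who did badly

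*Protocol*

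**What the plan says.** Two places remove women for doing worse.

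- Section F.3, item (6), in the exclusion list: "Women who experience worse outcomes than baseline two weeks after the study begins will be withdrawn from the study". It names no scale and no amount of worsening.
- Section H.1, on women who begin to show depression, self-harm or suicidality that the group therapist thinks warrants treatment: "they will be withdrawn from the study and referred to a hospital for alternative treatment". Other non-emergency deterioration is handled more softly; those women "will be closely monitored and, if appropriate, considered for referral for alternative treatment".

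The schedule has no outcome assessment at two weeks. Section E.5.B says "we will evaluate potential development of these adverse events at baseline, 8 weeks, and the 3-month follow-up", adds informal weekly monitoring, and says "Participants in the wait-list group will also be assessed for adverse events over the phone at 3 weeks and 6 weeks".

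The analyses affected are in Section G.3. Safety hypothesis A expects "lower proportions of suicidal ideation, suicide attempt, and self-mutilation at 8 weeks and 3-month follow-up, compared to baseline" within the AWARE group, tested by McNemar's test. The efficacy analysis is intention-to-treat, in which "all women who are randomized will be included for analysis". A further t-test compares outcome measures "between those who drop out versus those who complete the intervention".

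**The concern.** Item (6) can only operate after enrolment, so it is not an eligibility criterion. It is a withdrawal rule driven by the outcome. Both rules end participation in the study, not just attendance at sessions, and neither is paired with continued assessment. If staff follow the text, the missing 8-week and 3-month data will come disproportionately from women who worsened.

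McNemar's test uses only women measured at both times. A woman who develops ideation and is withdrawn drops out of the cell that counts against improvement, while women who improve stay in theirs. Hypothesis A is then tilted towards a fall, and a real rise is harder to see. Section D says the safety results will inform a larger study, so this is one of the pilot's stated products. Assessments that were never made cannot be recovered by a later analysis plan.

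**Working it through.** **Does any text keep withdrawn women under assessment?**

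- The paragraph on withdrawal from AWARE in Section H.1 covers women who choose to leave and mentions no assessments.
- The graded calls in Section E.5.B (repeated in H.2 and H.3) are safety contacts, not outcome assessments.
- Section F.4, steps 8 and 9, lists the end-of-intervention and 3-month assessments as part of participation and does not mention withdrawn women.
- The intention-to-treat sentence and the dropout t-test in Section G.3 say how data are used. They do not arrange for any to be collected.
- The mixed models use baseline, 8-week and 3-month values, so the two-week status that drives withdrawal is not in the model.

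**Inputs.** From the protocol: 48 women per arm, 15% dropout by week 8, significance level 0.05. The protocol gives no event rate, correlation or loss fraction. Assumed: ideation prevalence p of 15-40%, within-woman correlation phi = 0.4, and a fraction w of new-onset women lost.

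**1. How many women a literal item (6) removes.** On a continuous score with mean improvement d (in SD) and baseline to week-2 correlation r, the share worse than baseline is Φ(−d/√(2(1−r))).

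- d = 0: 50%, or 24 of 48.
- d = 0.2, r = 0.5 to 0.8: 42% to 38%, or 20 to 18 of 48.
- d = 0.5, r = 0.5 to 0.8: 31% to 21%, or 15 to 10 of 48.

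The planned dropout is 0.15 × 48 = 7.2.

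**2. McNemar test with no true change.** Each discordant cell has probability p(1−p)(1−phi). At p = 0.30 this is 0.30 × 0.70 × 0.6 = 0.126, so after dropout 48 × 0.85 × 0.126 = 5.1 women are expected in each direction. Simulated chance of a false significant fall (asymptotic / exact):

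| p | w = 0 | w = 0.25 | w = 0.40 | w = 0.50 |
|---|---|---|---|---|
| 0.15 | .024/.007 | .047/.014 | .072/.019 | .095/.025 |
| 0.20 | .023/.009 | .050/.021 | .081/.032 | .112/.044 |
| 0.30 | .021/.011 | .053/.027 | .090/.049 | .133/.072 |
| 0.40 | .022/.012 | .056/.033 | .100/.060 | .143/.088 |

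At p = 0.30 and w = 0.50, phi = 0.2 gives .164/.111 and phi = 0.6 gives .103/.031.

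One typical table is not made significant. At p = 0.30 about 5 v 5 pairs are expected; losing two new-onset women leaves 5 v 3, exact p = 0.73. Even 5 v 0 gives p = 0.0625.

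**3. Trigger at week 2 only.** With equal latent correlations among baseline, week 2 and week 8, 34-46% of women with new ideation at week 8 already have it at week 2.

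- Half of the new week-2 cases withdrawn (1.8-3.5 of 48): false fall 4-5%, exact 1-3%.
- All of them withdrawn (3.7-6.9 of 48): 6-12%, exact 2-7%.

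**4. A true rise.** With half of the new week-2 cases withdrawn, the chance of a significant rise drops from 23% to 12% for a rise from 20% to 30%, and from 71% to 48% for a rise from 15% to 35%. This takes the rise as complete by week 2; if only half of it has occurred by then, the loss is smaller but in the same direction. False falls are at most 1% here.

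**5. Between arms, no true effect, ANCOVA on baseline.**

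- Rule applied equally in both arms (trigger of more than 1 SD worse): bias at most 0.003 SD, false positives about 5%.
- Rule acting only in AWARE, more than 1 SD worse: bias 0.05-0.08 SD towards AWARE for r = 0.3 to 0.7 (0.03 SD at r = 0.8), false positives about 6%.
- Rule acting only in AWARE, any worsening: bias 0.16 SD at r = 0.3 and 0.21-0.22 SD for r = 0.5 to 0.8; false positives 15-27% over r = 0.5 to 0.8.

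**The case against.** The strongest reply is that loss of follow-up is inferred from silence. No sentence says assessments stop at withdrawal, the analysis is intention-to-treat, Section F.4 lists the assessments with no stated exception, remote assessment is allowed, and the comparison of dropouts with completers is most useful if outcomes exist for dropouts. The consent forms, which might describe follow-up after withdrawal, are not in the text at hand. Even so, both rules say the woman leaves the study, and nothing in the protocol separates stopping sessions from stopping assessments. The dropout comparison could also be run on baseline values.

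Several narrower points stand:

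- The screening list in Section F.4, step 3e, rightly omits item (6), which cannot be assessed at screening.
- The Section H.1 rule is a legitimate clinical safeguard, with decisions shared between therapist and principal investigator.
- Item (6) does not name ideation, so its link to hypothesis A is an assumption. The Section H.1 rule does name suicidality.
- The weekly adverse event log and the event proportions can still record an event that leads to withdrawal.
- With so few discordant pairs the exact test is the natural choice, and in the week-2 scenario with half withdrawn its false-fall rate is only 1-3%. For rarer events, such as attempts, it would be lower still.
- Wait-list women are telephoned at weeks 3 and 6, so fairly equal application across arms is possible.

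These points limit the size. None of them cancels item (6) or secures the assessments.

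**Conclusion.** The concern holds. The protocol contains two outcome-dependent withdrawals from the study and no provision for assessing those women afterwards. The main damage is to the within-arm suicidality test: the false-fall rate rises from about 2% to 5-14% if a quarter to a half of new-onset women are lost (exact test, about 1% to 1-9%), and a true rise is more likely to be missed. These figures depend on assumed prevalence, correlation and loss fractions.

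The randomised comparison is little affected if the rules act equally, or if only marked worsening triggers them. It would be affected noticeably if any worsening counted and the rule acted only in AWARE, and item (6) sets no threshold to exclude that reading. The instructions also differ between sections: E.5.B gives graded follow-up without withdrawal, H.2 and H.3 refer to more intensive care, and F.3 and H.1 withdraw. The same woman could be handled in different ways. This should be fixed before enrolment; it does not invalidate the design.

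**What to change.** Delete item (6) from the exclusion list in Section F.3. Reword the withdrawal text in F.3 and H.1 so that worsening or suicidality may lead to stopping sessions and referral as clinically needed, while every randomised woman in either arm who still consents and is clinically able remains in the 8-week and 3-month assessments and in the intention-to-treat analysis. Report events that lead to stopping in the log-based adverse event proportions, without imputing them into the McNemar pairs. Bring the stopping language in E.5.B, F.3, H.1, H.2 and H.3 into line. The clinical threshold for stopping sessions is for the investigators to set.

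The cost is an amendment to protocol and consent wording and some effort to retain women who stop sessions. The two assessments are already planned for each woman at $20 plus $4 each (Section F.4, steps 8 and 9).

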(AWARE): A Stage IA and IB Intervention Development Study to screen at least 400 women in the greater Boston area and recruit a total of 96 women who meet the criteria for PTSD and traumatic history. The 8-week intervention will be given group psychotherapy along with secure mobile messages. Adherence to group psychotherapy, utilization/satisfaction of text messages, and safety (suicidality and intimate partner violence) will be tested as feasibility outcomes. The efficacy will also be tested by measuring HIV-related outcomes and psychiatric symptoms and substance use at baseline, week 8, and 3 months to determine effect of the adapted intervention. There will be a Focus Group Feedback Discussion after the 8-week psychotherapy sessions to allow participants to comment on the effectiveness of the intervention. This integrative approach is innovative in multiple ways: (1) the study will be the first pilot RCT study to target traumatized API women, (2) it feasibly incorporates a culturally appropriate intervention, (3) it is designed to reduce HIV risk behavior, and (4) it tests the feasibility of mobile technology. It is our aim that these efforts will ultimately lead to the reduction of HIV transmission, suicidality, and psychiatric symptoms among API women.

Section D: Background/ Rationale/ Purpose

In the text box below provide the following study information

- Background information
- Study rationale
- Study objectives and/or hypotheses

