Background information: The proposed 3-year adaptation and pilot testing of the Asian Women’s Action for Resilience and Empowerment (AWARE): A Stage IA and IB Intervention Development Study consists of the following goals: (1) provide the original Seeking Safety (SS) ¹ curriculum to Asian Women Discussion Group members for feedback and revision; (2) fully develop the AWARE protocol (which will modify SS by integrating Project FIO² and our cultural component) for API women; (3) use a pilot two-armed RCT design to test the feasibility and safety of our adapted intervention in Year 2, comparing the AWARE intervention group (n=48) with the wait-list group (n =48); and (4) employ multiple measures of the same constructs using a repeated measures design (assessments at pre-test, 8 weeks, and 3-month follow-up). We chose an RCT design to (1) establish the validity of statistical testing to the maximum level and (2) minimize potential biases (known and unknown factors and characteristics of the intervention and control groups). We will obtain outcomes for feasibility, safety, and preliminary efficacy of the primary outcomes (HIV-related outcomes) and secondary outcomes (psychiatric symptoms, substance use). These feasibility, safety, and efficacy outcomes will allow us to better plan for a larger-powered study. We will conduct the focus groups and pilot RCT at Boston University, School of Social Work (BUSSW), MA.

Study rationale and significance: *There is a mental and sexual health crisis in the API community in the US, particularly among young women (ages 18-35). This proposed*

project is intended to deepen our national understanding of this crisis and move us toward highly innovative solutions. We propose to design an appropriate intervention that reduces mental and sexual health problems in this population. There are 3 significant reasons why this study should be funded for research:

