- a. The participant will be encouraged to call the local Psychiatric Emergency Service (PES).
- b. She will also be encouraged to discuss her feelings with family members or close friends.
- c. Follow-up contact will be provided by the therapist until risk is determined to be minimal.

(2) Moderate risk (e.g. suicidal ideation present with additional risk factors: moderate intent, low hope, possible plan and/or possible means).

- a. The participant will be encouraged to call the local Psychiatric Emergency Service (PES).
- b. If the participant refuses to call PES, we will enlist the assistance of a family member, roommate, or close friend to do so.
- c. If the participant refuses to enlist family, friends, or a roommate, or if they are not present, she will be encouraged to have the therapist call for her. Should the participant refuse, and if no one is in the home to ensure ongoing safety, the therapist will make the phone call against her will.
- d. A plan for removing from the home any means with which to commit suicide, preferably with the assistance of family or trusted other, will be developed.
- e. There will be continuous follow-up phone contact (with the therapist or [name]) ensuring the participant's safety throughout the day and then on a daily basis until risk is determined to be mild. Phone calls will then occur less frequently until risk is determined to be minimal. The participant will be told at the outset of participation that, if suicide risk is present and they cannot be reached by phone, the local safety authority or police will be called.

(3) High risk (e.g. suicidal ideation present with several additional risk factors: high intent, no hope, a definite plan, and current means).

- a. The participant will be encouraged to call the local emergency room (ER).
- b. If the participant refuses to call the local ER, she will be encouraged to allow the PI or therapist to make the ER call. Should the participant refuse, the therapist or PI will make the phone call against her will. They will send an ambulance or unit to the home.

Section F: Study Design and Procedures

F.1. Study Design (check all that apply)

- Randomized trial
- Non-randomized trial testing new or experimental procedures or interventions
- Survey, interview
- Focus groups
- Database review, record review
- Epidemiological research
- Secondary analysis of previously collected data
- Other (specify):

F. Eligibility Criteria

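### The two-week worsening rule in F.3 item (6) has no week-2 outcome assessment or criterion behind it and conflicts with the monitoring rule in H.1

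*Protocol*

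**What the plan says.** The rule is the last entry in the exclusion list of Protocol F.3: "Women who experience worse outcomes than baseline two weeks after the study begins will be withdrawn from the study". It gives no outcome, instrument, size of change, assessor or arm.

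The assessment schedule appears in several places. Section D gives "assessments at pre-test, 8 weeks, and 3-month follow-up". The Section C summary describes "measuring HIV-related outcomes and psychiatric symptoms and substance use at baseline, week 8, and 3 months". The adverse event text in E.5.B (repeated in H.2 and H.3) puts the formal safety evaluations at the same three times, "as well as informally monitoring participant condition on a weekly basis", and adds a weekly log kept by participants. For wait-list women it adds that they are "assessed for adverse events over the phone at 3 weeks and 6 weeks after the start of treatment for the intervention group".

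H.1 has two relevant sentences. Under one, women with depression, self-harm or suicidality that the group therapist thinks needs treatment are withdrawn and referred. Under the other, women not in an emergency but "showing symptoms of deterioration (as determined by the licensed therapist) will be closely monitored and, if appropriate, considered for referral for alternative treatment".

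G.3 compares adherence between arms by chi-square, relates baseline characteristics to attrition, compares drop-outs with completers by t-test, tests safety events before and after treatment in the AWARE arm by McNemar's test, and commits to an ITT analysis of all randomised women.

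**The concern.** A mandatory withdrawal rule needs something to measure, a point at which it applies, and one answer to what happens to the woman. Item (6) has no scheduled measurement at its stated time and no criterion, and H.1 gives a different answer for a woman it could cover. Staff would have to improvise the trigger and choose between two instructions.

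The statistical stake is that these withdrawals would depend on outcome. Adherence, attrition and safety are what this pilot is meant to deliver. If women leave because someone judged them worse, those figures partly reflect how the rule was read rather than how AWARE was tolerated. The text also says withdrawn from the study, not only from the sessions, so follow-up may be lost as well.

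**Working it through.** The protocol gives no figure for this rule, so there is none to reproduce. The check sets the passages side by side.

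1. **Is there a week-2 comparison with baseline?** Sections C and D and G.3 place outcomes at baseline, 8 weeks and 3 months. E.5.B places the formal safety evaluations at the same times. Week 2 offers only informal monitoring, therapist observation at sessions and the self-kept log. The log covers safety events, but it is not the C-SSRS or CTS2 used for the formal evaluation, so it gives no like-for-like comparison with baseline.

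2. **Is there a criterion?** No. There are three primary outcomes (HIV risk behaviour, HIV knowledge, self-efficacy) and two secondary domains (psychiatric symptoms, substance use). The item does not say which count, how many must be worse, or by how much.

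3. **Does it agree with H.1?** It conflicts with the sentence on non-emergency deterioration, which leads to monitoring and possible referral. It overlaps only partly with the withdrawal sentence, which is limited to depression, self-harm or suicidality and turns on the therapist's judgement, whereas item (6) is worded as automatic.

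4. **Is it placed where it can be applied?** F.3 lists what makes a woman ineligible, yet item (6) can apply only after entry. The working exclusion list in F.4 step 3e has five entries and omits it. F.4 step 6 sends the Year 2 trial participants through that same step.

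5. **Is the opportunity to detect worsening equal?** AWARE women attend weekly sessions with a therapist. The wait-list arm starts its sessions 3 months after the AWARE arm, and its scheduled safety calls before then are at weeks 3 and 6.

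6. **Where would the withdrawals enter the analysis?** They would count in the adherence and attrition analyses in G.3. The drop-out versus completer comparison becomes partly circular if some women were removed because they were worse. McNemar's test needs both measurements on each woman; if early worseners have no later one, the remaining pairs lean towards improvement. In the mixed models, the state that led to withdrawal was never scored, so the model has no week-2 value to condition on.

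7. **Scale.** Planned drop-out to week 8 is 15%: 0.15 × 48 = 7.2 women per arm. G.3 does not say whether this includes withdrawals under item (6). One withdrawal changes an arm's adherence by 1/48 = 2.1 percentage points.

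**The case against.** The best defence is that item (6) is a safety precaution in a small pilot, that weekly therapist contact and the log give staff something to act on at week 2, and that H.1 already allows withdrawal at the therapist's discretion. Part of this stands. Week 2 is not without information, and the H.1 withdrawal sentence points the same way as item (6) for some women. It does not supply a comparison with baseline or remove the conflict with the monitoring sentence. Nor is this detail that a SAP would settle, since a withdrawal rule belongs in the protocol.

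A reader might infer four stronger claims that the documents do not support.

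- **The rule can operate in the AWARE arm only.** Item (6) refers to women without naming an arm. The log and weekly monitoring in E.5.B are worded for participants generally, and the wait-list calls read as an addition to them. F.4 item 9e does list the wait-list log beside that arm's own delayed sessions, so the text is ambiguous. Unequal opportunity is as far as it goes.
- **Many women would be withdrawn through chance variation in a score.** That needs a week-2 score, and none is scheduled. Any percentage would describe a procedure the protocol does not contain.
- **The mild suicide-risk procedure in E.5.B contradicts item (6).** It says "Follow-up contact will be provided by the therapist until risk is determined to be minimal", but not whether the woman stays enrolled. Contact is compatible with withdrawal.
- **Withdrawal removes care.** H.1 refers women withdrawn for the symptoms it names to alternative treatment, and the E.5.B follow-up is not made conditional on enrolment.

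**Conclusion.** The point holds in a limited form. Item (6) cannot be carried out as written, because it calls for a comparison with baseline at a time when no outcome or formal safety assessment is scheduled, and it sets no criterion. It contradicts one H.1 sentence, only partly overlaps the other, and is filed among eligibility criteria although it applies after entry. The passages must be reconciled.

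The possible distortion of the adherence, attrition and completer results follows from withdrawals that depend on outcome combined with unequal contact between arms. Distortion of the safety tests and the ITT analysis requires one further condition: that withdrawn women are not assessed at 8 weeks and 3 months. The protocol does not say either way. The number affected is unknown, so the point rests on the text and not on an estimated rate. It should be corrected, but it does not undermine the design as a whole.

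**What to change.** - Take item (6) out of the F.3 exclusion list and reconcile it with both H.1 sentences, so that one consistent rule covers a woman who deteriorates without an emergency. State the basis for comparison with baseline and whether the rule applies to both arms. The content of that rule is for the sponsor and IRB.
- Record withdrawals under the rule with their own reason code, and report them by arm, separately from voluntary drop-out, in the adherence, attrition and completer analyses.
- State that women withdrawn under the rule stay in the 8-week and 3-month assessments where they agree, in line with the ITT statement in G.3.

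The cost is protocol and consent wording plus one field on the data form. Continued follow-up uses assessments already scheduled and paid for in the plan, so no visit is added.
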